#### 4.4 Clinical Risks/Benefits of OBI-999

OBI-999 is an ADC composed of a humanized monoclonal IgG1 antibody conjugated with MMAE. Toxicities may include myelosuppression and neuropathy as these side effects have been observed with other ADCs based on the MMAE molecule. A complete discussion of guidance for the investigator is provided in the OBI-999 Investigator Brochure.

The risk-to-benefit ratio for this study is considered acceptable based upon the patient population, the available limited treatment options for patients with advanced solid tumors, the toxicology results and activity data observed in the preclinical safety studies, and the results of the Dose Escalation Phase of this study.

As of 02 June 2020, 13 out of 15 patients enrolled in Part A had an investigator driven tumor response assessment. The best overall response per Response Evaluation Criteria in Solid Tumors version 1.1 (RECIST 1.1) criteria was stable disease, which was observed in 5 patients, including 1 patient from Cohort 1 (0.4 mg/kg with rectal cancer), 2 patients from Cohort 2 (0.8 mg/kg; 1 with pancreatic cancer and 1 with esophageal cancer), and 2 patients from Cohort 3 (1.2 mg/kg; 1 with head and neck cancer and 1 with cancer of the appendix). However, due to the limited sample size in Part A (Dose-Escalation), a relationship between Globo H expression level and depth of clinical activity at the Recommended Phase 2 Dose (RP2D) has yet to be established in this patient population. This relationship will be further evaluated in Part B of the study at the RP2D of 1.2 mg/kg.

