7. SAMPLE SIZE AND POWER CALCULATION

This is a 2-part study: Part A (Dose-Escalation) and Part B (Cohort-Expansion).

Up to 30 patients were to have been enrolled in the 3+3 dose-escalation portion of the study (Part A).

The cohort-expansion portion of the study (Part B) will enroll up to 57 patients based on Simon's two-stage design. The first stage will recruit up to 9 patients in each of three cohorts. If at least 1 objective response is observed, a second stage recruitment will occur with up to 10 additional patients enrolled into that cohort, for a total of up to 19 patients per cohort. If at least 4 objective responses are observed in the 19 patients, then OBI-999 will be considered worthy of further evaluation in that indication. Patients will be followed up to the 24-week scheduled response assessment for the purposes of counting objective responses for Simon's two-stage design success criteria. This design is based on a level of low interest for a treatment with an ORR of 10% versus a level of high interest for a treatment with an ORR of 25%. The sample size is based on a one-sided alpha of 0.12 and 72% power. The two-stage design limits the number of patients treated for a treatment with low levels of activity.

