CR	PD	SD provided minimum criteria for SD duration met, otherwise PD
CR	NE for all subsequent time points	SD provided minimum criteria for SD duration met, otherwise NE
PR	CR	PR
PR	PR	PR
PR	SD	SD
PR	PD	SD provided minimum criteria for SD duration met, otherwise PD
PR	NE for all subsequent time points	SD provided minimum criteria for SD duration met, otherwise NE
NE	NE	NE

[1] If a CR is truly met at first timepoint, then any disease seen at a subsequent timepoint, even disease meeting PR criteria relative to baseline, makes the disease PD at that point (since disease must have re-appeared after CR). Best response would depend on whether minimum duration of SD was met. However, sometimes 'CR' may be claimed when subsequent scans suggest small lesions were likely still present and in fact the patient had PR, not CR at the first timepoint. Under these circumstances, the original CR should be changed to a PR and the best response is PR.

Objective Response Rate (ORR) is defined as the percentage of patients with confirmed PR or CR based on tumor assessment as determined by RECIST 1.1 among all the patients in the safety and efficacy populations. A confirmed response will be defined as two or more consecutive assessments separated by at least 3 weeks. For summaries in the safety population, patients who discontinue due to toxicity or clinical progression prior to post-baseline tumor assessments will be considered as non-responders and retained in the denominator. A summary with the number of patients by BOR categories, ORR and the Clopper-Pearson 95% confidence interval (CI) for the ORR will be provided.

A by-patient swim lane plot of time (weeks) to Overall Response will be provided, along with waterfall plots (bar plot) showing the best reduction in target lesion therapy will be presented for Cohort-Expansion patients.

Sample code for ORR is provided below:

```
proc freq data=data;
by cohort;
tables AVAL/binomial alpha=0.05 nocum norow;
exact binomial;
run;
```

If the BOR used for ORR based on unconfirmed and confirmed overall responses differs by 10%, then we will present the same summary for ORR based on unconfirmed overall responses as a sensitivity analysis.

B. Clinical Benefit Rate

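### The SAP's sample code for ORR names no response level and does not define its variable, so it may not return the ORR that the text defines

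*SAP*

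**What the plan says.** SAP section 10.7.1, Part B, item A (Objective Response) sets the target in words: "Objective Response Rate (ORR) is defined as the percentage of patients with confirmed PR or CR based on tumor assessment". On reporting, it says: "A summary with the number of patients by BOR categories, ORR and the Clopper-Pearson 95% confidence interval (CI) for the ORR will be provided".

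The sample code that follows calls "proc freq data=data", splits the data with a BY statement on cohort, requests "tables AVAL/binomial alpha=0.05 nocum norow", and ends with "exact binomial". It has no LEVEL= sub-option, no ORDER= option and no step that keeps a response level with a count of zero. Neither document says how AVAL is coded, or whether it is a responder flag or the best overall response itself.

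SAP section 7 gives the planned cohort size: "The first stage will recruit up to 9 patients in each of three cohorts". SAP section 11 keeps ORR, in the safety population, for the abbreviated report and drops CBR, DOR and PFS.

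**The concern.** With BINOMIAL and no named level, PROC FREQ estimates the proportion in the first level of the table. Here that level is decided by sort order and by which values happen to occur in a cohort, not by the definition of response. The code can therefore print a figure that contradicts the definition just above it.

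ORR is a Part B primary endpoint and the only response rate left in the abbreviated report. A cohort without responders, where a two-level AVAL fails under every coding, is a realistic case. In Part A, at the cut of 02 June 2020, Protocol section 4.4 reports: "The best overall response per Response Evaluation Criteria in Solid Tumors version 1.1 (RECIST 1.1) criteria was stable disease". A swapped rate in a cohort with some responders is harder to notice, because it can look plausible.

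**Working it through.** The SAP states no ORR result, so there is no figure of its own to reproduce. The check follows the code under each possible meaning of AVAL and compares the output with the ORR as defined.

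**Inputs**
- Planned stage 1 cohort size 9, full cohort size 19, ORR of low interest 10% and of high interest 25%: SAP section 7.
- Two-sided 95% level (alpha 0.05), one table per cohort, no level named: sample code, SAP section 10.7.1.
- Assumption: the standard SAS default, by which BINOMIAL without LEVEL= uses the first level present in ascending order of the unformatted values. This was emulated, not run in SAS.
- Assumption: the coding of AVAL, which the documents do not give. All plausible cases are shown.

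**Interval.** For x of n, the Clopper-Pearson limits are the 0.025 quantile of Beta(x, n−x+1) and the 0.975 quantile of Beta(x+1, n−x). The lower limit is 0 if x = 0 and the upper limit is 1 if x = n. For x = 0 the upper limit is 1 − 0.025^(1/n); for n = 9 this is 1 − 0.6637 = 0.3363.

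**Case 1: two levels, non-response sorts first** (0/1, N/Y, No/Yes). The code reports the non-response rate.

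| Responders | ORR as defined (95% CI) | Code output (95% CI) |
|---|---|---|
| 1/9 | 11.1% (0.3 to 48.2%) | 8/9 = 88.9% (51.8 to 99.7%) |
| 4/19 | 21.1% (6.1 to 45.6%) | 15/19 = 78.9% (54.4 to 93.9%) |

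**Case 2: two levels, response sorts first** (for example 1 = responder, 2 = non-responder). With at least one responder in the cohort, the output is the correct ORR.

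**Case 3: two levels, any coding, no responder in the cohort.** The BY group holds only the non-response value, so that value is the first level.

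| Responders | ORR as defined (95% CI) | Code output (95% CI) |
|---|---|---|
| 0/9 | 0% (0 to 33.6%) | 9/9 = 100% (66.4 to 100%) |
| 0/19 | 0% (0 to 17.6%) | 19/19 = 100% (82.4 to 100%) |

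**Case 4: AVAL holds best overall response as text.** The levels sort as CR, NE, PD, PR, SD, and the output is the share of whichever comes first among those present. For 5 PD, 3 SD and 1 PR the code gives PD, 5/9 = 55.6% (21.2 to 86.3%), against an ORR of 1/9 = 11.1%. For 1 CR, 2 PR and 6 SD it gives CR, 1/9 = 11.1%, against an ORR of 3/9 = 33.3%. The two agree only if there is at least one CR and no PR.

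**How likely is a cohort with no responder?** For a planned cohort of 9 and true ORR p, the probability is (1−p)^9. For at least one of three independent cohorts with the same p, it is 1 − [1 − (1−p)^9]^3.

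| True ORR | One cohort of 9 | At least one of three |
|---|---|---|
| 10% | 0.9^9 = 38.7% | 1 − (1 − 0.387)^3 = 77.0% |
| 25% | 0.75^9 = 7.5% | 1 − (1 − 0.075)^3 = 20.9% |

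Actual cohort sizes may differ: SAP section 5.4 records two replacement patients in the pancreatic cohort. If that made 9 + 2 = 11 patients, 0/11 would print as 100% (71.5 to 100%) instead of 0% (0 to 28.5%).

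**The case against.** The code is labelled as a sample, and the text beside it gives the numerator, the interval method and the populations correctly. A programmer who follows the text would have to correct the code. The coding of AVAL may be set in programming documents outside this set, and a coding that sorts responders first works whenever a responder exists. The default behaviour of SAS is assumed here, not tested. The best overall response counts appear in the same summary as the ORR, so a cohort with no CR and no PR beside an ORR of 100% would look wrong at once. The waterfall plot kept for the report offers a further cross-check.

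These points stand, and they set the severity. They do not make the code right: none of the codings considered gives the defined ORR in every cohort.

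A reader might infer three stronger things that the documents do not support:
- **That a cohort without responders prints 100% whatever the coding.** This holds for a two-level AVAL only. With multi-level best response, the output is the share of the first category present.
- **That the reported ORR will be wrong.** The documents do not show the production program or the coding.
- **That a go/no-go decision was affected.** The Simon rule counts responders and does not use this interval, and SAP section 5.4 says that the formal analysis never took place.

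The Part A result is only indirect support for a cohort without responders. It covers 13 of 15 patients at an interim date, while 22 were enrolled in the end, and Part A did not select on Globo H.

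**Conclusion.** The concern holds as a low-severity code correction. The sample code does not reliably compute the ORR and interval that the same section defines. It is correct for a two-level AVAL with responders sorted first and at least one responder in the cohort. Otherwise it gives the non-response rate, 100% for a cohort without responders (two-level AVAL), or the share of one response category (multi-level AVAL).

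Where it fails, the error is large: 88.9% for 11.1% at 1/9, and 100% for 0% at 0/9. The conclusion rests on the standard SAS default and on the code being used as printed. The probabilities of a cohort without responders also assume 9 patients per cohort and, for the three-cohort figures, independent cohorts with a common ORR.

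**What to change.** In SAP section 10.7.1:

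1. State that AVAL is a two-level responder flag and give its coding, for example 1 = confirmed CR or PR and 0 = otherwise, with patients lacking data set to 0 as section 10.3 already requires.
2. Name the response level, for example `tables AVAL / binomial(level='1') alpha=0.05`.
3. Keep the empty level. Supply one row per cohort and response level with its count, including zero counts, and add `weight count / zeros`. LEVEL= alone does not work when no responder is present in the cohort.

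Instead of steps 2 and 3, compute the Clopper-Pearson limits directly from the number of responders and N with the beta quantiles.

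The cost is a few lines of code and one sentence of text. No data, population, endpoint or decision rule changes. Testing the program on a cohort with no responder and on one with a single responder would confirm the change.

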10.7.2 SECONDARY ENDPOINTS

PART A (DOSE-ESCALATION)

A. PK parameters of OBI-999 and its active metabolite MMAE.

PK analyses will be conducted by OBI Pharma, Inc. Please refer to the SAP developed by OBI for PK parameters (Appendix III).

PART B (COHORT-EXPANSION)

A. TEAEs/TESAEs and laboratory abnormalities as graded by NCI CTCAE version 5.0*.

Please refer to the analysis presented to Section 9.7.1.

B. PK parameters of OBI-999 and its active metabolite MMAE.

PK analyses will be conducted by OBI Pharma, Inc. Please refer to statistical analysis plan developed by OBI for PK parameters (Appendix III).

10.7.3 EXPLORATORY ENDPOINTS

A. Potential predictive biomarkers for OBI-999 activity such as expression of Globo H and other tumor-associated glycans or tumor molecular phenotypes.

The above analysis will be conducted by OBI Translational Biology (or their designee). Details of these analyses will be provided in separate document(s). The results will be compiled into a separate appendix in Section 14 of the Clinical Study Report (CSR).

10.8 SAFETY ENDPOINTS

This section describes the safety endpoints that are not part of the primary, secondary or

exploratory endpoints previously described in section 9.7.

All safety endpoints will be analyzed using the safety population.

Safety will be evaluated by presenting summaries of exposure to study treatment, laboratory evaluations (hematology, chemistry, coagulation, and urine analysis), vital signs, electrocardiogram (ECG) and other parameters.

10.8.1 EXPOSURE TO STUDY TREATMENT AND TREATMENT COMPLIANCE

The number of doses received, number of doses adjusted along with reasons of dose adjustment, total actual dose received in mg, total planned dose in mg, percentage of compliance (defined below), number of infusions interrupted along with reasons for infusion interruptions; number of infusions prematurely discontinued along with reasons for infusion prematurely discontinued, and the extent of exposure (calculated as last dose date – first dose date +1), will be summarized using descriptive statistics by study part, cohort, and overall.

Percentage of compliance for a patient will be defined as the total actual dose received divided by the total planned dose multiplied by 100.

$$\text{Percentage of compliance (\%)} = \frac{\text{Total actual dose received in mg}}{\text{Total planned dose in mg}} \times 100$$

Extent of exposure will also be summarized categorically by number and percentages for each of the following categories and cumulatively according to these categories:

- > 0 and ≤ 3 weeks
- > 3 and ≤ 6 weeks
- > 9 and ≤ 12 weeks
- > 12 and ≤ 18 weeks
- > 18 and ≤ 24 weeks
- > 24 and ≤ 36 weeks
- > 36 and ≤ 48 weeks
- > 48 weeks

In addition, the percentages of compliance will be presented by the specific ranges for each study part and cohort:

- < 80%
- ≥ 80% to < 120%
- ≥ 120%

Data listings will be produced for all study drug administration data.

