**Table 8-1 OBI-999 Dose Modifications for Toxicity**

Toxicity	Hold Dose	% of Full Dose after Recovery to Grade 0-1
Grade 1	Do not hold dose	100
Grade 2	Hold dose until resolution to Grade 0 or 1	75
Grade 3	Hold dose until resolution to Grade 0 or 1	75
Grade 4	Treatment should be discontinued	Not applicable

Once the dose has been reduced for toxicity and found to be well tolerated, re-escalation may be permitted at the Investigator's discretion. If a patient requires dose reductions on more than 2 occasions for toxicity related to OBI-999, the patient should discontinue from the study.

All reasons for treatment modifications should be fully explained.

The study drug dose which is not administered within the permitted window period of  $\pm 3$  days, must be skipped, and the next dose will be administered as per protocol schedule. Any skipped dose due to safety reason and if medically justified, for OBI-999 treatment related or unrelated reasons, will not be captured as a protocol deviation for this study.

Treatment interruption for more than 2 consecutive doses for related or unrelated reasons may necessitate discontinuation of study treatment.

Treatment interruption for intercurrent non-treatment related AEs will be at the Investigator's discretion and based on the well-being of the patient. All reasons for treatment interruption and

delays should be fully explained. Treatment for hematologic and non-hematologic toxicity may be implemented as clinically indicated according to institutional guidelines. Refer Table 8-2 for therapeutic antiemetic and anti-diarrheal recommendations.

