5.1.1 PART A – DOSE-ESCALATION

Twenty-two patients with advanced solid tumors were enrolled in Part A. No Globo H expression testing was required for inclusion.

Five cohorts of escalating dose levels of 0.4, 0.8, 1.2, 1.6, and 2.0 mg/kg (capping calculations at a maximum of 100 kg) OBI-999 were planned to be enrolled and assessed using a 3+3 design to identify the MTD and RP2D. The RP2D of OBI-999 was determined to be 1.2 mg/kg (capping administered dose to a maximum of 120 mg for 100 kg) administered on Day 1 of each 21-day cycle.

Three patients were enrolled at the lowest dose level. If none of the 3 patients experienced a dose-limiting toxicity (DLT) in the first 21-day cycle, the next cohort of 3 patients was enrolled at the next higher dose level. If 1 of 3 patients in the initial dose cohort experienced a DLT, that cohort was expanded to 6 patients. If only 1 of these 6 patients had a DLT, the next cohort of 3 patients was enrolled at the next higher dose level. If 2 or more patients of the 3-6 patients in a cohort experienced a DLT, dose-escalation ceased, and the lower dose level was designated the MTD, where no more than 1 of 6 patients experienced at DLT. New patients were enrolled at the previous lower (tolerated) dose level until that cohort had 6 patients. This lower dose level was considered the MTD if ≤ 1 in 6 patients had a DLT.

A patient who withdraws from the study within the DLT evaluation period for reasons other than drug-related adverse event (AE) were replaced.

Escalation to higher OBI-999 dose cohorts is not permitted during the study. After a DLT is experienced by a patient, dose interruption, modifications, or dose delays may apply, as per Investigator judgement (refer protocol Section 8.3).

Patients will continue to receive treatment with OBI-999 until disease progression, unacceptable toxicity, consent withdrawal, or for up to 35 cycles (approximately 2 years), whichever occurs first.

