10. ANALYTICAL PLAN AND STATISTICAL METHODS

10.1 GENERAL CONVENTIONS AND STATISTICAL CONSIDERATIONS

All statistical analyses will be performed, and data appendices will be created using the SAS system version 9.4 or higher.

Data collected in this study will be presented in patient data listings and summary tables.

Descriptive statistics (number of patients with non-missing values, mean, standard deviation [SD], median, minimum, and maximum) will be presented for continuous variables. All raw data will be presented to the original number of decimal places. Means and medians will be presented to 1 more decimal place than in the raw data. Standard deviations will be presented to 2 more decimal places than in the raw data. Descriptive summaries of time to event data will include medians and confidence intervals.

All data will be listed for all patients.

Frequency distributions (counts and percentages) together with mean and SD of ordinal scores will be presented for categorical variables. Discrete variables that are ordinal scaled (e.g., Eastern Cooperative Oncology Group [ECOG] performance score) will additionally be presented with mean scores and SD. If not specified otherwise, the number of observations with non-missing values will be the denominator for percentage calculation. Further details on the handling of missing observations are given in section 9.3.

If days are converted to months, a factor of 30.4 days/month will be used. If days are converted to years, a factor of 365.25 days/year will be used. Time will be shown in study weeks, i.e., number of weeks from the first administration of any study drug.

Dose-Escalation (Part A). The dose-escalation analysis will be presented by OBI-999 dose (0.4, 0.8, 1.2, and 1.6 mg/kg) cohorts and overall. The following cohorts and overall will be presented:

- OBI-999 0.4 mg/kg
- OBI-999 0.8 mg/kg
- OBI-999 1.2 mg/kg
- OBI-999 1.6 mg/kg
- Dose-Escalation Total

OBI-999 2.0 mg/kg was planned but Part A was closed before this dose was administered, and therefore there no patients in this cohort. For this reason, this cohort will not be presented in any of the analyses.

Cohort-Expansion (Part B). The expansion part analysis will be presented by cancer type. The following cohorts and overall will be presented:

- Cohort 1: Pancreatic cancer
- Cohort 2: Colorectal cancer
- Cohort 3: Basket (any solid tumor type other than those included in Cohorts 1 and 2)
- Cohort-Expansion Total

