- In section §10.5, the protocol deviations will neither be summarized nor listed.
- In section §10.6.1, the baseline and demographic characteristics will be summarized using only the safety population and listed.
- In section §10.6.2, the medical history and current medical conditions will neither be summarized nor listed.
- In section §10.6.3, the prior and concomitant medications will neither be summarized nor listed.
- In section §10.6.4, the cancer history will be summarized using only the safety population and listed.
- In section §10.6.5, other medical history will not be listed.
- In section §10.6.6, prior cancer surgeries will neither be summarized nor listed.
- In section §10.6.7, prior cancer radiotherapy will neither be summarized nor listed.
- In section §10.6.8, prior cancer medication therapy will neither be summarized nor listed.
- In section §10.6.9, smoking history will neither be summarized nor listed.
- In section §10.7.1, adverse events that will be analyzed and listed have been marked with asterisks. Only ORR analysis using safety population and ADA analysis using safety and PK populations have been selected as CBR, DOR and PFS analyses will no longer be conducted for the aCSR. Only waterfall plot (bar plot) showing the best reduction in target lesion therapy will be presented for Cohort-Expansion patients.
- In section §10.8.1, only extent of exposure will be summarized, and all study drug administration data will be listed.
- In section §10.8.2, laboratory data will only be listed. OBI decided not to conduct normalization of local laboratory assessments; therefore, data will be listed as recorded.
- In section §10.8.3, vital signs data will only be listed.
- In section §10.8.4, electrocardiogram data will only be listed.
- In section §10.8.5, ECOG, physical examination and ophthalmological data will neither be summarized nor listed.

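### The exposure bands jump from 6 weeks to 9 weeks, so a patient with 43 to 63 days of exposure falls in no category

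*SAP*

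**What the plan says.** SAP Section 10.8.1 defines "extent of exposure (calculated as last dose date – first dose date +1") and asks for descriptive statistics. It then adds a banded table: "Extent of exposure will also be summarized categorically by number and percentages for each of the following categories and cumulatively according to these categories". In weeks, the eight bands listed are: over 0 to 3, over 3 to 6, over 9 to 12, over 12 to 18, over 18 to 24, over 24 to 36, over 36 to 48, and over 48. There is no row for other or unclassified values.

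Section 11 cuts most of Section 10.8.1 for the abbreviated report but keeps this part: "only extent of exposure will be summarized, and all study drug administration data will be listed". It does not drop the banded table.

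Two general rules bear on the percentages. Section 10.8 says "All safety endpoints will be analyzed using the safety population". Section 10.1 says "If not specified otherwise, the number of observations with non-missing values will be the denominator for percentage calculation".

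**The concern.** The bands should cover every possible exposure once, and they do not. The early bands are 3 weeks wide, matching the 21-day cycle, and the missing one is the only 3-week step absent before week 12. No reason is given, so this reads as a slip and not a choice.

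Three things follow for a patient in the gap:

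- **Bands.** The patient is counted in no band, so the band counts sum to less than the number of dosed patients.
- **Cumulative figures.** Running sums of the printed bands would be too low from the over 9 to 12 week band onward. Nested counts (all patients at or below 12 weeks, and so on) would be right. The SAP does not say which is meant.
- **Percentages.** If the non-missing rule is applied to exposure in days, the patient is in the denominator but in no numerator. If it is applied to the derived category, the patient leaves both, and the table appears complete on a reduced N.

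Under Section 11, laboratory, vital-sign and ECG data will only be listed. Exposure is therefore one of the few safety summaries left to give context to the adverse-event tables.

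**Working it through.** The plan states no figure to reproduce here. The check is whether the bands cover every possible exposure value.

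**Inputs**

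- Exposure in days = last dose date − first dose date + 1 (SAP 10.8.1). This equals the study day of the last dose.
- Bands as printed in SAP 10.8.1, with 1 week = 7 days.
- One dose every 21 days (SAP 5.2).
- Dosing window of ±3 days, with doses outside it skipped (Protocol 8.3, text after Table 8-1: "The study drug dose which is not administered within the permitted window period of" …). I read the window against the nominal dosing day, which is an assumption.

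**Edges of the gap**

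- The second band ends at 6 × 7 = 42 days.
- The third band starts above 9 × 7 = 63 days, so at day 64.
- Uncovered: days 43 to 63, which is 63 − 43 + 1 = 21 values.

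Testing every whole day from 1 to 799 against the eight bands confirms this. Days 43 to 63 match none, and every other day matches exactly one.

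**Who falls in it**

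On schedule, the last dose of k doses falls on day 21 × (k − 1) + 1.

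| Doses | Nominal day | Weeks | Band at nominal day | ±3-day range | Days in gap |
|---|---|---|---|---|---|
| 1 | 1 | 0.14 | over 0 to 3 | – | none |
| 2 | 22 | 3.14 | over 3 to 6 | 19–25 | none |
| 3 | 43 | 6.14 | **none** | 40–46 | 43–46 |
| 4 | 64 | 9.14 | over 9 to 12 | 61–67 | 61–63 |
| 5 | 85 | 12.14 | over 12 to 18 | 82–88 | none |

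The gap therefore takes in:

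- a third and last dose given on time or up to 3 days late;
- a fourth and last dose given 1 to 3 days early;
- a patient dosed on Days 1 and 43 with the Day 22 dose skipped.

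A third dose given 1 to 3 days early (days 40–42) is classified correctly.

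The result does not hinge on the exposure definition. If exposure ran to the end of the last cycle (last − first + 21), three doses would give 42 + 21 = 63 days, still in the gap.

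**Weight of one patient**

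- Part A ("Twenty-two patients with advanced solid tumors were enrolled in Part A"): 1/22 = 4.5%.
- A Part B stage 1 cohort, if filled to 9 and all dosed: 1/9 = 11.1%. The bands would then sum to 8/9 = 88.9%, or to 100% of an N of 8 if the patient were treated as missing.
- The pancreatic cohort with its 2 replacement patients (SAP 5.4), on the same assumption: 1/(9 + 2) = 9.1%.

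**With the band added**

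Inserting over 6 to 9 weeks puts every day from 1 to 799 in exactly one band, with no gap and no overlap.

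**The case against.** The strongest reply is that the effect is small and may be nil.

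- **Scan timing works against the gap.** Tumour scans fall every 6 weeks at first, within the week before the next cycle (Protocol Table 9-1, footnote p). Progression on the 6-week scan would normally come before dose 3, leaving the last dose at Day 22. Progression on the 12-week scan would normally come before dose 5, leaving it at Day 64. Both days are inside printed bands, so the gap mainly catches stops between scans. This stands as a point about frequency. The ±7-day scan window (Protocol Section 10), early fourth doses, and stops for toxicity or withdrawal mean the gap need not be empty.
- **Not all 21 days are equally reachable.** With the window read against the nominal day, only days 43–46 and 61–63 (7 of 21) can be a last dose given within the window. That is correct. These are counts of days, not probabilities of being affected.
- **The shrunken denominator is speculative.** Section 10.8 names the safety population, and a dosed patient has a non-missing exposure in days, so the patient should stay in the denominator. That is the more natural reading, but Section 10.1 does not rule out the other. The bands fail to sum under either.
- **The band may exist elsewhere.** The table shells are a separate document and were not available. A line lost when the PDF was converted to text cannot be fully excluded, though the list shows no break or redaction mark.

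These points limit the size and certainty of the effect. None supplies the missing band.

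**Conclusion.** The point holds. As written, the bands leave 43 to 63 days unclassified in a safety table that the abbreviated report keeps, and the gap includes the ordinary case of a patient stopping after three on-schedule doses.

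The consequence is minor. It affects a descriptive table only, by about 4.5% of Part A or 9% to 11% of a Part B cohort for each affected patient. The Part B figures assume that stage 1 filled to 9 and all patients were dosed. The number of affected patients is not given and could be zero.

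**What to change.** - In SAP Section 10.8.1, insert a band for more than 6 and up to 9 weeks between the second and third bands. Make the same change in the table shell if the band is missing there too.
- State that percentages use the safety-population N of each cohort.
- State that each cumulative count is the number of patients with exposure at or below the band's upper limit.
- Add a programming check that the bands sum to N in every cohort and in the totals.

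The cost is one band and two short clarifications in the SAP, at most one row in the shell, and a routine check. No new data are needed.

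The first and last items correct the error. The other two keep the table unambiguous if an exposure value is ever missing.
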